#### Pelvic Floor Disorder

				failure", "symptomatic failure", and "anatomic and symptomatic failure" where retreatment failure corresponds to retreatment for prolapse, symptomatic failure corresponds to bothersome vaginal bulge symptoms, and anatomic failure corresponds to prolapse beyond the hymen as described in the surgical failure under the permanent failure state assumption definition above. Retreatment failure type is prioritized above the anatomic and/or symptomatic failure types.
Indicator of surgical failure at post- operative visit under the transient failure state assumption	CRF-13, CRF-12, CRF- 14/37	Binary	1-, 2-, 3- , 4-, 5-years	At each timepoint, surgical failure under the transient failure state assumption is defined if any one of the three criteria (retreatment failure at that visit or any prior visit, anatomic failure at that visit, or symptomatic failure at that visit) is met at that visit.
				Participants not meeting the criteria for surgical failure at the timepoint will be considered not a surgical failure, regardless of missingness of the 3 components of the surgical outcome at the timepoint's corresponding attended post-operative visit.
				Participants who have discontinued from the study by timepoint's corresponding post-operative visit will be missing the transient failure state surgical outcome at the timepoint.
				Participants who missed the post-operative visit corresponding to the timepoint without a retreatment failure at any prior attended post-operative visit will also be missing the transient failure state surgical outcome at the timepoint.

				By this definition, a subject can be defined as a surgical failure at timepoints where the corresponding post- operative visit is missed IF the subject is still participating in the study and had a surgical failure due to retreatment failure at any prior attended post-operative visit (i.e. post- operative visits 6 months up to 60 months).
At-visit failure type	CRF-13, CRF-12, CRF- 14/37	Nominal Categorical (4 levels)	1-, 2-, 3- , 4-, 5-years	At each timepoint, subjects who experience a surgical failure under the transient failure state assumption, failure type will be defined for the surgical failure occurring at the timepoint.
				Each surgical failure will be categorized into the following 4 types: "retreatment failure", "anatomic failure", "symptomatic failure", and "anatomic and symptomatic failure" where retreatment failure corresponds to retreatment for prolapse, symptomatic failure corresponds to bothersome vaginal bulge symptoms, and anatomic failure corresponds to prolapse beyond the hymen as described in the surgical failure under the transient failure state assumption definition above. Retreatment failure type is prioritized above the anatomic and/or symptomatic failure types.
Indicator of retreatment (surgery or pessary) for prolapse	CRF-13	Binary	6-months through 60 months	Through the timepoint of follow-up, based on retreatment for pelvic organ prolapse as reported on the coordinator follow-up CRF-13 collected in 6-month intervals through 5 years, the indicator is defined as follows: 1 = Yes, if surgery or pessary is reported for questions A3a or A3b respectively at any attended post-operative visit

Pelvic Floor Disorder

				
 
0 = No, if subject attended at least one post-operative visit 6 months or after and reported no additional treatment (surgery or pessary) for pelvic organ prolapse was performed for question A1 across all attended post-operative visits. Subjects with missing responses to question A1 are included as long as the subject has at least one non-missing response (assuming low missing response rate among attended visits).
 
. = Missing, otherwise
 
*Note: Prior to and upon database lock, any other free text responses recorded on CRF-13 Question B5 "Since surgery, did you have a reoperation* (P)?" specifying retreatment for POP will be assessed, and if any, included in this definition at the discretion of the principal investigator.
 

Indicator of surgical retreatment for prolapse	CRF-13	Binary	6-months through 60 months	Through the timepoint of follow-up, based on retreatment for pelvic organ prolapse as reported on the coordinator follow-up CRF-13 collected in 6-month intervals through 5 years, the indicator is defined as follows:
				1 = Yes, if surgery is reported for question A3a at any attended post-operative visit
				0 = No, if subject attended at least one post-operative visit 6 months or after and reported no additional surgery treatment for pelvic organ prolapse was performed for question A1 or subject reported additional treatment for question A1 and the additional treatment

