#### **9.3** Efficacy Variables **Timepoint(s)** Variable Type Definition CRF Source **Primary Efficacy Outcome** 6 months through 60 Time to surgical CRF-13, Continuous Among subjects who experience a surgical failure (see months CRF-12, definition below) starting at the 6 month post-operative failure CRFvisit through their last attended ASPIRE visit, the time to surgical failure is defined as the number of months (i.e. 14/37 months as intended by the visit schedule) from the surgical intervention to first post-operative visit with surgical failure. Surgical failure is defined at each attended post-operative visit if any ONE of the following criteria is met: Retreatment failure is defined as retreatment for \_ prolapse via additional surgery or pessary as reported on coordinator follow-up CRF-13 Anatomic failure is defined as any prolapse beyond the hymen (i.e. POPQ points Ba, Bp, or C > 0.0 cm) as reported on the evaluator (blinded) follow-up CRF-12 during POPQ examination Symptomatic failure is defined as experiencing bothersome vaginal bulge symptoms as reported on CRF-14/37. Bothersome vaginal bulge symptoms are defined as a positive response to Question 3 Do you usually have a bulge or something falling out that you can see or feel in your vaginal area? AND any degree

of bother greater than "Not at all" (i.e. "Somewhat",
"Moderately", or "Quite a bit")
Participants not meeting the criteria for surgical failure at the attended post-operative visit will be considered not a surgical failure, regardless of missingness of the 3 components of the surgical outcome (i.e. retreatment failure, anatomic failure, and symptomatic failure).
The time to surgical failure will be missing for all participants who are considered not a surgical failure at each of the attended post-operative visits 6 months through their last attended ASPIRE visit scheduled in 6- month intervals up to 60 months.
Note that since ASPIRE followed participants until the last participant completed their 36 month visit, ASPIRE study completers have a varying amount of follow-up time from 36 to 60 months.
For survival analysis, participants with no failure by their last attended study visit are censored, and with follow-up duration equal to the number of months (i.e. months as intended by the visit schedule) corresponding to the last attended visit.

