#### **Pelvic Floor Disorder**

				
 
was not surgery as reported for question A3a across all attended post-operative visits.
 
Subjects with missing responses to question A1 are included as long as the subject has at least one non-missing response (assuming low missing response rate among attended visits).
 
. = Missing, otherwise
 

Indicator of pessary- only retreatment for prolapse	CRF-13	Binary	6-months through 60 months	Through the timepoint of follow-up, based on retreatment for pelvic organ prolapse as reported on the coordinator follow-up CRF-13 collected in 6-month intervals through 5 years, the indicator is defined as follows: 1 = Yes, if only pessary is reported for question A3b at any attended post-operative visit. Subjects with surgical retreatment and pessary retreatment for prolapse as reported for questions A3a and A3b respectively are not included here.
				0 = No, else if subject attended at least one post- operative visit 6 months or after and reported no additional pessary treatment or both surgery AND pessary treatment) for pelvic organ prolapse was performed for question A1 or subject reported additional treatment for question A1 and the additional treatment was not pessary as reported for question A3b across all attended post-operative visits. Subjects with surgical retreatment and pessary retreatment for prolapse as reported for questions A3a and A3b respectively are

				included here. Subjects with missing responses to question A1 are included as long as the subject has at least one non- missing response (assuming low missing response rate among attended visits). . = Missing, otherwise
Indicator of retreatment (surgical or non-surgical) for urinary incontinence	CRF-13	Binary	6-months through 60 months	Through the timepoint of follow-up, based on retreatment for urinary incontinence as reported on the coordinator follow-up CRF-13 collected in 6-month intervals through 5 years, the indicator is defined as follows:
				1 = Yes, if surgery, medications, pessary for incontinence, supervised pelvic muscle exercises, time voiding & fluid management, periurethral injection, Botox injection, e-stim, or other specified is reported for the A5 question group at any attended post-operative visit

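### A prolapse reoperation recorded only in CRF-13 B5 free text can count as retreatment but not as surgical retreatment, because the SAP 9.3 rows draw on different items

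*SAP*

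**What the plan says.** All the relevant definitions are in the efficacy-variable table of SAP 9.3.

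- **Any retreatment (surgery or pessary).** Coded Yes if surgery or pessary "is reported for questions A3a or A3b respectively at any attended post-operative visit". A note then extends the source to "any other free text responses recorded on CRF-13 Question B5", the item that asks about reoperation since surgery. Such text "specifying retreatment for POP will be assessed, and if any, included in this definition at the discretion of the principal investigator". The note places this both before and at database lock.
- **Surgical retreatment.** Coded Yes if surgery "is reported for question A3a at any attended post-operative visit". It is coded No when A1 reports no further surgery for prolapse, or when A1 reports treatment that "was not surgery as reported for question A3a across all attended post-operative visits". There is no B5 note.
- **Pessary-only retreatment.** Coded Yes if only a pessary "is reported for question A3b at any attended post-operative visit". Women are moved out of this row only when surgery is reported at A3a. There is no B5 note.
- **Primary outcome, retreatment component.** Defined as retreatment for "prolapse via additional surgery or pessary as reported on coordinator follow-up CRF-13". No question number is given. A woman who meets no criterion at an attended visit "will be considered not a surgical failure, regardless of missingness of the 3 components".
- **Permanent-state and transient-state failure indicators.** Both use the same three failure criteria. The transient version carries a retreatment forward to later visits.

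**The concern.** B5 asks about reoperation, so the surgical-retreatment row has the strongest claim to its content, yet that row never consults it. The B5 note is limited to its own definition, so a case accepted there does not pass to the neighbouring rows.

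Three things are at stake. First, a woman who had a second prolapse operation can be reported as not surgically retreated, or as managed by pessary only. Second, the any-retreatment count need not equal surgical plus pessary-only. Third, inclusion rests on one person's judgement with no written criteria and no stated masking, although the form comes from a coordinator whom the masking table (protocol Table 3, SAP 4.4.1) lists as unmasked.

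The need for subsequent procedures is a stated safety comparison across the three arms (protocol A.2.b and L.2). Readers will compare the surgical row between mesh and native tissue.

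**Working it through.** The plan gives no figure on this point, so there is none to reproduce. The check sets the definitions side by side and runs cases through them.

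**Step 1. Sources, from SAP 9.3.**

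| Variable | Set to Yes by | B5 text used? |
|---|---|---|
| Any retreatment | A3a or A3b | Yes, at discretion |
| Surgical retreatment | A3a | No |
| Pessary-only | A3b, unless A3a surgery | No |
| Primary retreatment component | Surgery or pessary reported on CRF-13, no item named | Not stated |
| Permanent and transient indicators | Same criteria as the primary outcome | Not stated |

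**Step 2. Cases.**

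| Woman | Any | Surgical | Pessary-only |
|---|---|---|---|
| Operation reported at A3a | Yes | Yes | No |
| Operation in B5 only; A1 negative, A3a and A3b blank | Yes if the investigator includes her, otherwise No | No | No |
| Operation in B5, pessary at A3b, nothing at A3a | Yes | No | Yes |

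In the second case, if she is included, the any-retreatment row gains 1 while surgical plus pessary-only gains 0 + 0, so the rows do not add up. In the third case the rows do add up (1 = 0 + 1), but an operated woman sits in the non-surgical category. A check of totals would not find her.

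**Step 3. Primary component.** It names the form and no item. B5 is on that form, so an operation for prolapse written there is surgery for prolapse reported on CRF-13. Read literally, both women are failures. However, the any-retreatment row also starts from treatment reported on CRF-13, then narrows to A1, A3a and A3b, and needs a separate note to reach B5. Naming the form does not tell a programmer which items to use.

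**Step 4. Size.** Input: 121 women planned per arm (protocol M.1, SAP 6). The shift in one arm's surgical-retreatment rate from k uncounted women is k/121. The value of k is not in the documents, so the range here is an assumption:

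- k = 0: no shift
- k = 1: 1/121 = 0.83 percentage points
- k = 2: 2/121 = 1.65 points
- k = 3: 3/121 = 2.48 points

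Both documents expect the transvaginal mesh arm to reach about 95% of plan: 0.95 × 121 ≈ 115. One woman there is 1/115 = 0.87 points.

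**The case against.** The strongest reply is that this is a wording gap between secondary rows. SAP 9.5.1 treats secondary efficacy results as descriptive, and SAP 7.7 says that their p-values are not judged for significance. CRF-13 itself is not in the documents. Skip patterns or edit checks may tie B5 to A1 and A3a, so that a B5-only case rarely or never occurs. SAP 7.5 also plans a masked review before lock that characterises individual failures by time and reason.

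Much of this stands. It limits the importance of the point, and the number of cases may be zero. It does not remove the inconsistency, because the rows conflict as written. The masked review does not name B5, and it starts from failures, so a woman not already flagged might never reach it. The SAP is more specific elsewhere: Dindo grade III or higher goes to masked review by the AE Adjudication Committee, and vaginal infections to a masked clinical review.

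A reader might go further and infer that a reoperated woman is scored a success in the primary analysis, which would bias the hazard ratios. The documents do not support that. The primary component cites the whole form, which covers B5. Time to failure runs to the first failing visit of any kind, so prolapse beyond the hymen or a bothersome bulge recorded earlier already counts her. A pessary reported at A3b is itself a failure. A lost event would need all of the following:

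- an operation recorded only in B5
- programming limited to A3a and A3b, or investigator discretion carried over and not exercised
- no pessary at A3b
- no anatomic or symptomatic failure at any visit

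None of these is documented.

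**Conclusion.** The point holds for the three retreatment indicators. As SAP 9.3 is written, a B5-only prolapse reoperation can be any-retreatment Yes and surgical retreatment No, and it can be pessary-only Yes when a pessary is also reported. Whether it enters the any-retreatment row through B5 depends on discretion with no stated criteria or masking.

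The size is about 0.8 percentage points on an arm's surgical-retreatment rate per woman, taking 121 women as the denominator. The total is unknown and may be nil. It rests on the assumption that CRF-13 allows B5 to be completed without A3a.

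For the primary outcome the conclusion is narrower. The literal rule already counts such a woman as a failure, but the items behind it are not named and should be aligned with the other rows. No effect on the primary hazard ratio is shown.

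**What to change.** Define one retreatment variable: surgery at A3a, pessary at A3b, or B5 text stating an operation for prolapse. Have the B5 text adjudicated masked to arm before lock, against a written criterion. Use the variable in:

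- the any-retreatment, surgical and pessary-only rows, where a B5 prolapse operation sets surgical to Yes and pessary-only to No
- the retreatment component of the primary outcome (SAP 9.3 and 9.4.1)
- the permanent-state and transient-state failure indicators and their failure types

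Report the number of B5-only cases by arm.

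If lock has passed, document which CRF-13 items fed each variable, including the primary component, and show the retreatment rows with B5-only cases counted. This second route probably applies, since SAP 12, dated 20 February 2023, already gives event counts by arm. Reviewers who do not see the arm can still adjudicate the text.

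The cost is a few lines of SAP wording or an addendum and a short review of free text already collected. No new data are needed.

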#### **Pelvic Floor Disorder**

				
 
was not surgery as reported for question A3a across all attended post-operative visits.
 
Subjects with missing responses to question A1 are included as long as the subject has at least one non-missing response (assuming low missing response rate among attended visits).
 
. = Missing, otherwise
 

Indicator of pessary- only retreatment for prolapse	CRF-13	Binary	6-months through 60 months	Through the timepoint of follow-up, based on retreatment for pelvic organ prolapse as reported on the coordinator follow-up CRF-13 collected in 6-month intervals through 5 years, the indicator is defined as follows: 1 = Yes, if only pessary is reported for question A3b at any attended post-operative visit. Subjects with surgical retreatment and pessary retreatment for prolapse as reported for questions A3a and A3b respectively are not included here.
				0 = No, else if subject attended at least one post- operative visit 6 months or after and reported no additional pessary treatment or both surgery AND pessary treatment) for pelvic organ prolapse was performed for question A1 or subject reported additional treatment for question A1 and the additional treatment was not pessary as reported for question A3b across all attended post-operative visits. Subjects with surgical retreatment and pessary retreatment for prolapse as reported for questions A3a and A3b respectively are

				included here. Subjects with missing responses to question A1 are included as long as the subject has at least one non- missing response (assuming low missing response rate among attended visits). . = Missing, otherwise
Indicator of retreatment (surgical or non-surgical) for urinary incontinence	CRF-13	Binary	6-months through 60 months	Through the timepoint of follow-up, based on retreatment for urinary incontinence as reported on the coordinator follow-up CRF-13 collected in 6-month intervals through 5 years, the indicator is defined as follows:
				1 = Yes, if surgery, medications, pessary for incontinence, supervised pelvic muscle exercises, time voiding & fluid management, periurethral injection, Botox injection, e-stim, or other specified is reported for the A5 question group at any attended post-operative visit
				0 = No, else if subject attended at least one post- operative visit 6 months or after and reported no additional treatment for urinary incontinence was performed for question A4 across all attended post-operative visits. Subjects with missing responses to question A4 are included as long as the subject has at least one non-missing response (assuming low missing response rate among attended visits).
				. = Missing, otherwise

Anatomic POPQ point Ba measurement	CRF-12	Continuous	6-, 12-, 18-, 24-, 30-, 36-, 42-, 48-, 54-, 60- months	At each timepoint, POPQ point Ba as reported on the evaluator (blinded) follow-up CRF-12 during POPQ examination at the timepoint's corresponding attended post-operative visit.
Anatomic POPQ point Bp measurement	CRF-12	Continuous	6-, 12-, 18-, 24-, 30-, 36-, 42-, 48-, 54-, 60- months	At each timepoint, POPQ point Bp as reported on the evaluator (blinded) follow-up CRF-12 during POPQ examination at the timepoint's corresponding attended post-operative visit.
Anatomic POPQ point C measurement	CRF-12	Continuous	6-, 12-, 18-, 24-, 30-, 36-, 42-, 48-, 54-, 60- months	At each timepoint, POPQ point C as reported on the evaluator (blinded) follow-up CRF-12 during POPQ examination at the timepoint's corresponding attended post-operative visit.
Anatomic POPQ point GH measurement	CRF-12	Continuous	6-, 12-, 18-, 24-, 30-, 36-, 42-, 48-, 54-, 60- months	At each timepoint, POPQ point GH as reported on the evaluator (blinded) follow-up CRF-12 during POPQ examination at the timepoint's corresponding attended post-operative visit.
Anatomic POPQ point Aa measurement	CRF-12	Continuous	6-, 12-, 18-, 24-, 30-, 36-, 42-, 48-, 54-, 60- months	At each timepoint, POPQ point Aa as reported on the evaluator (blinded) follow-up CRF-12 during POPQ examination at the timepoint's corresponding attended post-operative visit.
Anatomic POPQ point Ap measurement	CRF-12	Continuous	6-, 12-, 18-, 24-, 30-, 36-, 42-, 48-, 54-, 60- months	At each timepoint, POPQ point Ap as reported on the evaluator (blinded) follow-up CRF-12 during POPQ examination at the timepoint's corresponding attended post-operative visit.
Anatomic POPQ point Pb measurement	CRF-12	Continuous	6-, 12-, 18-, 24-, 30-, 36-, 42-, 48-, 54-, 60- months	At each timepoint, POPQ point Pb as reported on the evaluator (blinded) follow-up CRF-12 during POPQ

				examination at the timepoint's corresponding attended post-operative visit.
Anatomic total vaginal length (TVL) measurement	CRF-12	Continuous	6-, 12-, 18-, 24-, 30-, 36-, 42-, 48-, 54-, 60- months	At each timepoint, total vaginal length (TVL) as reported on the evaluator (blinded) follow-up CRF-12 during POPQ examination at the timepoint's corresponding attended post-operative visit.
Indicator of anatomic POPQ point C measurement > -2/3 of anatomic total vaginal length (TVL)	CRF-12	Binary	6-, 12-, 18-, 24-, 30-, 36-, 42-, 48-, 54-, 60- months	At each timepoint, based on POPQ point C and total vaginal length (TVL) as reported on the evaluator (blinded) follow-up CRF-12 during POPQ examination at the timepoint's corresponding attended post-operative visit, the indicator is defined as follows:
measurement ("Apical Descent")				1 = Yes, if POPQ point C > -2/3 x TVL, both POPQ point C and TVL are non-missing
				0 = No, else if POPQ point C <= -2/3 x TVL, both POPQ point C and TVL are non-missing
				. = Missing, otherwise
Maximum extent of prolapse: leading edge of Ba, Bp, C,	CRF-12	Continuous	6-, 12-, 18-, 24-, 30-, 36-, 42-, 48-, 54-, 60- months	At each timepoint, POPQ maximum value of points Ba, Bp, or C reported on the evaluator (blinded) follow-up CRF-12 during POPQ examination at the timepoint's corresponding attended post-operative visit.
Change from baseline in PFDI-20 UDI subscale	PFDI-20	Continuous	6-, 12-, 24-, 36-, 48, 60- months	The PFDI-20 UDI subscale score will be computed at baseline and at each timepoint's corresponding attended post-operative visit during which assessments are administered and collected using standard scoring algorithms (Barber 2006). Specifically, average the responses for questions Q15 through Q20 (0=no, 1=yes: not at all, 2=yes: somewhat, 3=yes: moderately, 4=yes: quite a bit) and multiply by 25. If there are missing

				responses, then the score is the average of the non- missing responses multiplied by 25. The outcome will then be computed as the difference in score at each timepoint's corresponding attended post-operative visit and the score at baseline. If data for the assessment are missing at a timepoint's corresponding attended post- operative visit, the outcome variable will be coded as missing.
Change from baseline in PFDI-20 CRADI subscale	PFDI-20	Continuous	6-, 12-, 24-, 36-, 48, 60- months	The PFDI-20 CRADI subscale score will be computed at baseline and at each timepoint's corresponding attended post-operative visit during which assessments are administered and collected using standard scoring algorithms (Barber 2006). Specifically, average the responses for questions Q7 through Q14 (0=no, 1=yes: not at all, 2=yes: somewhat, 3=yes: moderately, 4=yes: quite a bit) and multiply by 25. If there are missing responses, then the score is the average of the non- missing responses multiplied by 25. The outcome will then be computed as the difference in score at each timepoint's corresponding attended post-operative visit and the score at baseline. If data for the assessment are missing at a timepoint's corresponding attended post- operative visit, the outcome variable will be coded as missing.
Change from baseline in PFDI-20 POPDI subscale	PFDI-20	Continuous	6-, 12-, 24-, 36-, 48, 60- months	The PFDI-20 POPDI subscale score will be computed at baseline and at each timepoint's corresponding attended post-operative visit during which assessments are administered and collected using standard scoring algorithms (Barber 2006). Specifically, average the responses for questions Q1 through Q6 (0=no, 1=yes: not

				at all, 2=yes: somewhat, 3=yes: moderately, 4=yes: quite a bit) and multiply by 25. If there are missing responses, then the score is the average of the non-missing responses multiplied by 25. The outcome will then be computed as the difference in score at each timepoint's corresponding attended post-operative visit and the score at baseline. If data for the assessment are missing at a timepoint's corresponding attended post-operative visit, the outcome variable will be coded as missing.
Change from baseline in PFDI-20 Global Score	PFDI-20	Continuous	6-, 12-, 24-, 36-, 48, 60- months	The PFDI-20 Global Score will be computed at baseline and at each timepoint's corresponding attended post- operative visit during which assessments are administered and collected using standard scoring algorithms (Barber 2006). Specifically, sum the scores from the UDI, CRADI, and POPDI subscales. The outcome will then be computed as the difference in score at each timepoint's corresponding attended post-operative visit and the score at baseline. If data for the assessment are missing at a timepoint's corresponding attended post-operative visit, the outcome variable will be coded as missing.
Change from baseline in PFIQ-7 UIQ subscale	PFIQ-7	Continuous	6-, 12-, 24-, 36-, 48, 60- months	The PFIQ-7 UIQ subscale score will be computed at baseline and at each timepoint's corresponding attended post-operative visit during which assessments are administered and collected using standard scoring algorithms (Barber 2006). Specifically, average the responses for questions Q1a through Q7a (0=not at all, 3=quite a bit) and multiply by 100/3. If there are missing responses, then the score is the average of the non- missing responses multiplied by 100/3. The outcome will then be computed as the difference in score at each

				timepoint's corresponding attended post-operative visit and the score at baseline. If data for the assessment are missing at a timepoint's corresponding attended post- operative visit, the outcome variable will be coded as missing.
Change from baseline in PFIQ-7 CRAIQ subscale	PFIQ-7	Continuous	6-, 12-, 24-, 36-, 48, 60- months	The PFIQ-7 CRAIQ subscale score will be computed at baseline and at each timepoint's corresponding attended post-operative visit during which assessments are administered and collected using standard scoring algorithms (Barber 2006). Specifically, average the responses for questions Q1b through Q7b (0=not at all,, 3=quite a bit) and multiply by 100/3. If there are missing responses, then the score is the average of the non- missing responses multiplied by 100/3. The outcome will then be computed as the difference in score at each timepoint's corresponding attended post-operative visit and the score at baseline. If data for the assessment are missing at a timepoint's corresponding attended post- operative visit, the outcome variable will be coded as missing.
Change from baseline in PFIQ-7 POPIQ subscale	PFIQ-7	Continuous	6-, 12-, 24-, 36-, 48, 60- months	The PFIQ-7 POPIQ subscale score will be computed at baseline and at each timepoint's corresponding attended post-operative visit during which assessments are administered and collected using standard scoring algorithms (Barber 2006). Specifically, average the responses for questions Q1c through Q7c (0=not at all, , 3=quite a bit) and multiply by 100/3. If there are missing responses, then the score is the average of the non-missing responses multiplied by 100/3. The outcome will then be computed as the difference in score at each

				timepoint's corresponding attended post-operative visit and the score at baseline. If data for the assessment are missing at a timepoint's corresponding attended post- operative visit, the outcome variable will be coded as missing.
Change from baseline in PFIQ-7 Global Score	PFIQ-7	Continuous	6-, 12-, 24-, 36-, 48, 60- months	The PFIQ-7 Global Score will be computed at baseline and at each timepoint's corresponding attended post- operative visit during which assessments are administered and collected using standard scoring algorithms (Barber 2006). Specifically, sum the scores from the UIQ, CRAIQ, and POPIQ subscales. The outcome will then be computed as the difference in score at each timepoint's corresponding attended post-operative visit and the score at baseline. If data for the assessment are missing at a timepoint's corresponding attended post-operative visit, the outcome variable will be coded as missing.
Indicator of improvement based on Patient Global	PGII	Binary	6-, 12-, 24-, 36-, 48, 60- months	At each timepoint, based on PGII as reported on the PGII at the timepoint's corresponding attended post-operative visit, the indicator is defined as follows:
Impression of Improvement (PGII)				1 = Yes, if improvement of 1=very much better or 2=much better are reported on the PGII
				0 = No, else if improvement of 3=a little better,, 7=very much worse are reported on the PGII
				. = Missing, otherwise
Change from baseline in PISQ-IR sexually active – average score	PISQ-IR	Continuous	6-, 12-, 24-, 36-, 48, 60- months	The PISQ-IR sexually active – average score will be computed at baseline and at each timepoint's corresponding attended post-operative visit during which assessments are administered and collected using

standard scoring algorithms for the IUGA method
(Constantine 2017). Specifically, for subjects with a
sexual partner (i.e. Q12: 1=yes) sum the scores for
questions Q7, Q8a-c, Q9, Q10, Q11, Q13, Q14a-b, Q15,
Q16, Q17, Q18, Q19a-c, Q20a-d using reverse scores for
Q8b-c, Q9, Q11, Q14a-b, Q16, Q17, Q18, and Q19a-c
(Q7, Q8a-c, Q9, Q11: 1=never,, 5=[almost] always;
Q10: 1=much less intense,, 5=much more intense; Q13:
1=all of the time,, 4=hardly ever/rarely; Q14a-b:
1=very positive,, 4=very negative; Q15: 1=never,,
5=always; Q16: 1=daily,,5=never; Q17: 1=very high,
, 5=very low or none at all; Q18: 1=not at all,, 4=a
lot; Q19a-c: 1=satisfied,, 5=dissatisfied; Q20a-d:
1=strongly agree,, 4=strongly disagree). If there are
more than 10 missing responses, then a total score is not
calculated. Similarly, for subjects without a sexual partner
(i.e. Q12: 2=no) sum the scores as described above
excluding Q13 and Q14a-b from the sum as these
questions are not collected among subjects without a
sexual partner. If there are more than 9 missing responses,
then a total score is not calculated. To handle missing
values, the final score is obtained by dividing the sum by
the number of items answered. The outcome will then be
computed as the difference in score at each timepoint's
corresponding attended post-operative visit and the score
at baseline. If data for the assessment are missing at a
timepoint's corresponding attended post-operative visit,
the outcome variable will be coded as missing. Scores
should only be calculated for participants that are
sexually active.
bonduny uotivo.

Change from baseline in Functional Activity Assessment Scale (FAS) overall score	AAS	Continuous	6-, 12-, 24-, 36-, 48, 60- months	The Functional Activities Assessment Scale (FAS) score will be computed at baseline and at each timepoint's corresponding attended post-operative visit during which assessments are administered and collected using standard scoring algorithms (McCarthy 2005). Specifically, sum the scores for questions Q1,, Q13 (1=no difficult,, 5=not able to do it; responses of 6=did not do it for other reasons will not be included in the sum). If there are more than 6 missing responses, then a total score is not calculated. To handle missing values, the raw score is obtained by dividing the sum by the number of items answered. The final score is obtained by scaling the raw score to range from 0 to 100 using the following formula: (65 – raw score)/52 x 100 Note: 65 is the maximum raw score, and 52 is the range of possible scores (65-13=52). The outcome will then be computed as the difference in score at each timepoint's corresponding attended post- operative visit and the score at baseline. If data for the assessment are missing at a timepoint's corresponding attended post-operative visit, the outcome variable will be coded as missing.
Change from baseline in SF-12 physical component PCS Subscale	SF-12	Continuous	6-, 12-, 24-, 36-, 48, 60- months	At baseline and at each timepoint, based on physical component items as reported on the SF-12 at the timepoint's corresponding attended post-operative visit, the scoring of the physical component subscale is defined in Attachment 1 .

				The outcome will then be computed as the difference in score at each timepoint's corresponding attended post- operative visit and the score at baseline. If data for the assessment are missing at a timepoint's corresponding attended post-operative visit, the outcome variable will be coded as missing.
Change from baseline in SF-12 mental component MCS Subscale	SF-12	Continuous	6-, 12-, 24-, 36-, 48, 60- months	At baseline and at each timepoint, based on mental component items as reported on the SF-12 at the timepoint's corresponding attended post-operative visit, the scoring of the mental component subscale is defined in Attachment 1 .
				The outcome will then be computed as the difference in score at each timepoint's corresponding attended post- operative visit and the score at baseline. If data for the assessment are missing at a timepoint's corresponding attended post-operative visit, the outcome variable will be coded as missing.
Indicator of new or worsening stress urinary incontinence (SUI)	CRF-12, CRF-13, CRF-96	Binary	surgery through 3 years	Through the timepoint of follow-up, based on the Adverse Event Log (CRF-96) or specific complications as reported on the masked post-operative CRF-12 and coordinator follow-up CRF-13 collected at 6-weeks and in 6-month intervals through 3 years, the indicator is defined as follows:
				1 = Yes, if new or worsening SUI is reported as evident (i.e. response of "AE", "SAE") on any of the complication tables as described above or "Stress urinary incontinence"" in the term reported on the AE Log

				0 = No, else if subject attended at least one post- operative visit 6 weeks or after and complication(s) of interest specified above are reported as "Not Evident" across all attended post-operative visits. Subjects with missing responses are included as long as the subject has at least one "Not Evident" response (assuming low missing response rate among attended visits).
				. = Missing, otherwise
				*Note: Prior to and upon database lock, any stress urinary incontinence events identified by the MedDRA coded preferred term "stress urinary incontinence") with start date after surgery collected ONLY on the AE log and not reported on any of the complications tables will be assessed, and if any, included in this definition at the discretion of the principal investigator.
Indicator of new or worsening urgency urinary incontinence (UUI)	CRF-12, CRF-13, CRF-96	Binary	surgery through 3 years	Through the timepoint of follow-up, based on the Adverse Event Log (CRF-96) or specific complications as reported on the masked post-operative CRF-12 and coordinator follow-up CRF-13 collected at 6-weeks and in 6-month intervals through 3 years, the indicator is defined as follows:
				1 = Yes, if new or worsening UUI is reported as evident (i.e. response of "AE", "SAE") on any of the complication tables as described above or "Urge incontinence" in the term reported in the AE log.

				0 = No, else if subject attended at least one post- operative visit 6 weeks or after and complication(s) of interest specified above are reported as "Not Evident" across all attended post-operative visits. Subjects with missing responses are included as long as the subject has at least one "Not Evident" response (assuming low missing response rate among attended visits).
				
 
. = Missing, otherwise
 
*Note: Prior to and upon database lock, any new or worsening urgency urinary incontinence events identified by the MedDRA coded preferred term "urgency urinary incontinence" ) collected ONLY on the AE log with start date after surgery and not reported on any of the complications tables will be assessed, and if any, included in this definition at the discretion of the principal investigator.
 

Indicator of new or worsening fecal incontinence (FI)	CRF-12, CRF-13, CRF-96	Binary	surgery through 3 years	Through the timepoint of follow-up, based on the Adverse Event Log (CRF-96) or specific complications as reported on the masked post-operative CRF-12 and coordinator follow-up CRF-13 collected at 6-weeks and in 6-month intervals through 3 years, the indicator is defined as follows:
				1 = Yes, if new or worsening FI is reported as evident (i.e. response of "AE", "SAE") on any of the complication tables as described above or "Fecal incontinence" in the term reported in the AE log.

				0 = No, else if subject attended at least one post- operative visit 6 weeks or after and complication(s) of interest specified above are reported as "Not Evident" across all attended post-operative visits. Subjects with missing responses are included as long as the subject has at least one "Not Evident" response (assuming low missing response rate among attended visits).
				. = Missing, otherwise
				*Note: Prior to and upon database lock, any new or worsening fecal incontinence events identified by the MedDRA coded preferred term "fecal incontinence" ) with start date after surgery collected ONLY on the AE log and not reported on any of the complications tables will be assessed, and if any, included in this definition at the discretion of the principal investigator.
